## 1.2. Overview of known potential risks

Historical and current anecdotal data on use of convalescent plasma suggest it is safe in coronavirus infection. Therefore, the large number of exposed healthcare workers, public servants and first responders, in combination with the high mortality of COVID-19, particularly in elderly and vulnerable persons, strongly argue that the benefits of convalescent serum outweigh its possible risks in high risk exposed individuals and/or those with early disease. However, for all cases where convalescent plasma administration is considered, a risk-benefit assessment must be conducted to assess individual variables.

The theoretical risk involves the phenomenon of antibody-mediated enhancement of infection (ADE). ADE can occur for several viral diseases and involves an enhancement of disease in the presence of certain antibodies. For coronaviruses, several mechanisms for ADE have been described and there is the theoretical concern that antibodies to one type of coronavirus could enhance infection to another viral strain (Wan et al., 2020). It may be possible to predict the risk of ADE of SARS-CoV-2 experimentally, as proposed for MERS. Since the proposed use of convalescent plasma in the COVID-19 epidemic would rely on preparations with high titers of neutralizing antibody against the same virus, SARS-CoV-2, ADE may be unlikely. The available evidence from the use of convalescent plasma in patients with SARS1 and MERS (Mair-Jenkins et al., 2015), and anecdotal evidence of its use in patients with COVID-19 (Xinhua, 2020), suggest it is safe. Nevertheless, caution and vigilance will be required in for any evidence of enhanced infection.

Another theoretical risk is that antibody administration to those exposed to SARS-CoV-2 may avoid disease but modify the immune response such that those individuals mount attenuated immune responses, which would leave them vulnerable to subsequent re-infection. In this regard, passive antibody administration before vaccination with respiratory syncytial virus was reported to attenuate humoral but not cellular immunity (Crowe, Firestone, & Murphy, 2001). This concern will be investigated as part of this clinical trial by measuring immune responses in those exposed and treated with convalescent plasma to prevent disease. If the concern proved real these individuals could be vaccinated against COVID-19 when a vaccine becomes available.

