## 3 STATISTICAL CONSIDERATIONS

### 3.1 Design Overview

This is a double-blinded, randomized phase 2 trial to evaluate the efficacy and safety of human SARS-CoV-2 immune plasma in individuals who are close contacts to person with COVID-19 within 7 days according to the CDC definition. This will also serve as an internal pilot in the seamless phase 2/3 study.

Eligible participants will be randomized to receive high-titer anti-SARS-CoV-2 immune plasma or control (albumin 5%) in a 2:1 ratio. We plan to enroll a total of 150 participants, with a maximum of 100 receiving the plasma and 50 receiving the control.

Each participant will be followed for 28 days after randomization and treatment, and will be tested and evaluated at baseline and on Days 3, 7, 14, 28 using a seven-category severity scale:

1. Not hospitalized, negative PCR for SARS-CoV-2
2. Not hospitalized, positive PCR for SARS-CoV-2 without symptom
3. Not hospitalized, positive PCR for SARS-CoV-2 with symptoms
4. Non-ICU hospitalization, not requiring supplemental oxygen
5. Non-ICU hospitalization, requiring supplemental oxygen
6. Requiring mechanical ventilation and/or in ICU
7. Death

The primary study endpoint is the rating on Day 28, or last rating evaluated. We will also consider time to various dichotomizations on this scale as secondary

outcomes, including time to death, time to requiring critical care, and time to requiring hospitalization

Other endpoints include:

- Anti-SAR-CoV-2 titers (Days 3, 7, 14, 28, 90 in addition to baseline)
- SAR-CoV-2 PCR positivity (Days 0, 3, 7, 14, 28 in addition to baseline)
- SAR-CoV-2 RNA (Days 0, 3, 7, 14, 28 in addition to baseline)

Exploratory objective:

- To assess the correlation between SARS-CoV-2 PCR positivity from nasal swab specimens, based on RT PCR, and detection of viable SARS-CoV-2 from nasal swab specimens based on viral culture assays

Serious adverse events, and grades  $\geq 3$  adverse events will be monitored during the study period.

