## 3.2 Statistical Analysis

Primary Analysis and go/no-go decision: The severity scale of the two groups will be compared using stratified, Mann Whitney test. Specifically, a one-sided  $P < 0.15$  favoring the immune plasma arm will constitute a “go decision” in this phase 2 trial, suggesting evidence of promise for further investigation in an expanded Phase 3 study. The results in this trial will then be used to plan the Phase 3 sample size, with possibility that the data in this Phase 2 trial will be included in the final analysis using adjusted  $P$  values. Details of sample size re-estimation and adjusted analysis, as well as the final statistical analysis plan, will be determined before unblinding the study data.

This analysis will be intent-to-treat. Given the short study duration and the nature of the treatment, however, we anticipate minimal non-compliance and loss to follow-up.

Subgroup Analysis: If the stratified analysis reaches the go decision, with  $P < 0.15$ , we will explore the treatment effect within each stratum using Mann Whitney test.

Secondary Analyses: All secondary efficacy analyses will be intent-to-treat. Time-to-event variables (e.g. time to death) will be analyzed using Cox proportional hazard model. Longitudinal data collected over multiple days (e.g., PCR positivity) will be analyzed using generalized linear mixed models. Treatment effects on these variables will be estimated with 95% confidence intervals.

Safety Analyses: Serious adverse events will be summarized by grades and types using proportions and 95% confidence intervals for the two study arms, and the two arms will be compared using Fisher's exact test.

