### 3.3 Power Consideration

Assuming a shift odds ratio of 2 under a proportional odds model on the severity rating scale, with a sample size of 150, the study will have 74% to 80% power of reaching the go decision in the scenarios we considered. The actual power will depend the distribution of the severity scale in the control arm. Table 2 gives the power of the two extreme scenarios: Scenario 1 describes scenario with higher rates for more severe outcomes, and Scenario 2 with majority of participants remaining or becoming PCR negative; the outcome distributions are identical between the two strata in these scenarios. We have evaluated the power for in-between scenarios and scenarios where non-infected and infected strata are different; the power is within the range 74% and 80% in all scenarios we have considered.

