## **7.3 Halting Criteria for the Study**

The study enrollment and dosing will be stopped and an ad hoc review will be performed if any of the specific following events occur or, if in the judgment of the study physician, subject safety is at risk of being compromised:

1. Unexpected death of a dosed subject in relation to infusion
2. Occurrence of a life-threatening allergic/hypersensitivity reaction (anaphylaxis), manifested by bronchospasm with or without urticaria or angioedema requiring hemodynamic support with pressor medications or mechanical ventilation.
3. One subject with an unexpected SAE associated with study product.
4. Two subjects with a Grade 3 or higher toxicity for the same parameter associated with study product.
5. An overall pattern of symptomatic, clinical, or laboratory events that the DSMB consider associated with study product and that may appear minor in terms of individual events but that collectively may represent a serious potential concern for safety.
6. Any other event(s) which is considered to be a serious adverse event in the good clinical judgment of the responsible physician. This will be appropriately documented.

Furthermore, given that ADE may be an issue with convalescent antibody treatment, out of an abundance of caution we will monitor the number of subjects in each trial arm that progresses to an indication for need of mechanical ventilation. In monitoring the number of subjects that progresses to this stage, we will present these data to the DSMB masked so that they may objectively evaluate and determine whether they would like to be unmasked. After at least 50% of trial participants have accumulated follow-up, the number of subjects that progress to this stage will be presented to the masked DSMB and formally asked whether they (1) see a clinically meaningful difference between trial arms that trigger an unmasking of the

DSMB and (2) if so do they require a formal interim analysis. At any point should the DSMB asked to be unmasked and require a formal interim analysis, we will examine the difference in treatment arms for need for mechanical ventilation. This interim analysis will adjust for factors related to need for mechanical ventilation including age and presence of cardiopulmonary comorbidities.

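### The interim check for antibody-mediated enhancement (ADE) looks only at need for mechanical ventilation, too rare at about 75 participants to show or adjust for a general worsening of disease; the severity rating should be added beside it

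*Combined protocol and SAP*

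**What the plan says.** Section 1.2 names ADE as the theoretical risk of the product and says that it "involves an enhancement of disease in the presence of certain antibodies".

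Section 7.3 sets up a dedicated check for it: "we will monitor the number of subjects in each trial arm that progresses to an indication for need of mechanical ventilation". The counts go to the DSMB masked. Once at least half of the participants have follow-up, the DSMB is asked whether it sees a clinically meaningful difference, and if so whether it requires a formal interim analysis. In that analysis "we will examine the difference in treatment arms for need for mechanical ventilation", with adjustment for age and cardiopulmonary comorbidities. No test, significance level, harm effect or power is given for this comparison.

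Section 3.1 says that each participant "will be tested and evaluated at baseline and on Days 3, 7, 14, 28 using a seven-category severity scale". The Schedule of Events and Sections 4.3 to 4.9 add ratings on Days 1 and 60. Categories 4 and 5 are hospitalisation without and with oxygen. Category 6 is ventilation and/or ICU, and category 7 is death.

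Two other provisions bear on harm. Section 3.2 compares serious adverse events between arms by Fisher's exact test, with no interim timing. Section 7.1 gives the DSMB a quarterly review of safety and efficacy data.

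**The concern.** The risk is stated as worsening of disease, but the formal question to the DSMB, and the analysis it can trigger, count one event near the top of the scale. A new admission or a new need for oxygen does not enter that comparison. In Table 2's control arms these are twice as common as ICU/ventilation plus death: 10% + 10% = 20% against 5% + 5% = 10% in Scenario 1, and 4% + 4% = 8% against 2% + 2% = 4% in Scenario 2.

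If plasma made disease generally worse, the ventilation counts at half follow-up would usually show nothing clear. The DSMB could then take the absence of a difference as reassurance, although the data that could show such a pattern are already collected.

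**Working it through.** **Inputs from the documents.** Section 3.1: "We plan to enroll a total of 150 participants, with a maximum of 100 receiving the plasma and 50 receiving the control". Control distributions: Table 2. Section 3.3: "Assuming a shift odds ratio of 2 under a proportional odds model on the severity rating scale, with a sample size of 150", stated there for benefit.

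**Assumptions, because Section 7.3 gives no figures.**
- The look falls at half of each arm, 50 v 25.
- Harm is the same odds ratio of 2, reversed so that plasma is worse.
- The test is one-sided at 0.05.
- Table 2, which describes the Day 28 or last rating, stands in for the rating at the look.
- Category 6 stands in for ventilation. It is the nearest label, but it also includes ICU stays without ventilation and leaves out ventilated patients who died. Category 6 or 7 is therefore shown as a more generous version.

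**Reproducing the plan's own power.** Simulating the tie-corrected Mann-Whitney test at 100 v 50 and one-sided 0.15 gives 74 to 75% in Scenario 1 and 80.5 to 81% in Scenario 2. Table 2 states 74% and 80%, so the inputs are read correctly.

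**Plasma distribution under harm.** For each cut k, odds of category k or worse in plasma = 2 × control odds. Example, Scenario 1, category 6 or worse: 0.10/0.90 = 0.111; × 2 = 0.222; 0.222/1.222 = 0.182.

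| | 1–3 | 4 | 5 | 6 | 7 |
|---|---|---|---|---|---|
| Scenario 1 control | 0.70 | 0.10 | 0.10 | 0.05 | 0.05 |
| Scenario 1 plasma | 0.538 | 0.128 | 0.152 | 0.087 | 0.095 |
| Scenario 2 control | 0.88 | 0.04 | 0.04 | 0.02 | 0.02 |
| Scenario 2 plasma | 0.786 | 0.066 | 0.071 | 0.038 | 0.039 |

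**Expected counts at the look, both arms together.**
- Category 6, Scenario 1: 25 × 0.05 + 50 × 0.087 = 1.25 + 4.35 = 5.6.
- Category 6, Scenario 2: 25 × 0.02 + 50 × 0.038 = 0.5 + 1.9 = 2.4.
- Category 6 or 7: 2.5 + 9.1 = 11.6 and 1.0 + 3.8 = 4.8.
- Categories 4 to 7: 25 × 0.30 + 50 × 0.462 = 30.6 and 25 × 0.12 + 50 × 0.214 = 13.7.

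The planned model needs at least three coefficients (arm, age, comorbidity). That leaves 5.6/3 = 1.9 or 2.4/3 = 0.8 category 6 events per coefficient. The ordinal rating has about 31 or 14 informative participants, which is better, although 14 is still thin.

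**Power, odds ratio 2 harm, 50 v 25, one-sided 0.05 (simulation, unadjusted tests).**

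| Comparison | Scenario 1 | Scenario 2 |
|---|---|---|
| Mann-Whitney on {1–3}, 4, 5, 6, 7 | 39–40% | 25% |
| Category 6 or 7, score test | 23–24% | 7% |
| Category 6 or 7, Fisher | 13% | 1% |
| Category 6 alone, score test | 8% | 1% |

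**If harm is confined to categories 6 and 7** (binary odds ratio 2, one-sided 0.05).

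| Extra severe cases drawn from | Scenario | Ordinal | Category 6 or 7, score | Category 6 or 7, Fisher |
|---|---|---|---|---|
| Categories 4–5 | 1 | 6.7% | 23.5% | 12.6% |
| Categories 4–5 | 2 | 4.4% | 7.2% | 1.3% |
| Categories 1–5 in proportion | 1 | 16.0% | 23.5% | 12.6% |
| Categories 1–5 in proportion | 2 | 9.7% | 7.1% | 1.3% |

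**If some participants start in category 5.** Inclusion criteria 4 and 7 allow entry in hospital and on oxygen. The documents give no share, so a range is shown. Using the raw worst rating, ordinal power under the odds ratio 2 shift is:

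| Share starting in category 5 | Scenario 1 | Scenario 2 |
|---|---|---|
| 0 | 40% | 25% |
| 20% | 30% | 16% |
| 40% | 24% | 12% |
| 60% | 21% | 11% |

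The score test on category 6 or 7 stays near 24% and 7% throughout.

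**The case against.** The strongest reply is that ventilation is a deliberate choice. It is specific to severe harm, and because it counts progression under a cap on oxygen at entry, it is largely unaffected by who was already in hospital. A raw worst rating would score a participant enrolled on oxygen as category 5 for good. This stands: any ordinal comparison has to account for baseline category, and ventilation should stay.

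The look is also a DSMB judgement, with no significance threshold for opening the analysis. The DSMB sees other data, and halting criterion 5 covers overall patterns. This stands too, and limits the point to what is formally asked and analysed.

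A reader might infer three stronger things that the documents do not support:
- *That the check loses a fixed 16 to 27 points of power.* The differences in the power table against category 6 or 7 do span about that range. They rest on a proportional-odds harm, a significance level and an event definition that Section 7.3 does not state. Section 3.3 assumes proportional odds only for benefit, and for tail-only harm the sign can change.
- *That the plan cuts its own severity scale.* Need for ventilation is a separate progression count, and no rate is given for it.
- *That this is the only between-arm harm comparison.* It is the only formal interim one. Section 3.2 compares serious adverse events, which by the definition in Section 6.7 include hospitalisation.

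**Conclusion.** The point holds in a limited form. The formal ADE question and the interim analysis that may follow rest on ventilation alone. Under Table 2 and a doubling of the odds of worse disease, about 6 or 2 to 3 category 6 events are expected at about 75 participants. That is too few for a reliable adjusted binary comparison, and even category 6 or 7 would give only about 12 or 5.

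Against a general shift in severity, the ordinal rating is clearly the more sensitive measure, although at 39 to 40% and 25% it is not powerful either. Against harm limited to the most severe outcomes, the binary event can do better, most clearly in Scenario 1. The two measures cover different patterns of harm, and the documents do not say which to expect, so the rating should be added and should not replace ventilation. All power figures use unadjusted tests and Day 28 distributions; the documents give no distribution for the worst rating.

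**What to change.** In Section 7.3:
- Show the DSMB, with the ventilation counts, the by-arm distribution of each participant's worst post-infusion clinical category (1–3 pooled, 4, 5, 6, 7), tabulated by baseline category. Pooling 1–3 keeps PCR status from driving a harm comparison.
- State that any formal interim analysis will report a proportional-odds comparison of that rating, adjusted for baseline category, age and cardiopulmonary comorbidities, alongside the planned ventilation comparison. A plain Mann-Whitney test would drop the adjustment that Section 7.3 requires.
- State that both comparisons belong to one interim analysis, because the section ties the final significance level to the number of such analyses.

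The cost is a few sentences and one more DSMB table, with no new data, visits or participants. The downside is small: the ordinal comparison is less specific to the most severe harm, and the DSMB has two harm measures to weigh instead of one.

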Upon completion of this review, DSMB will determine if study entry or study dosing should be interrupted or if study entry and study dosing may continue according to the protocol. Should the trial not be stopped at this time point, the final analysis would need to account the number of interim analyses that were conducted.

Therefore, we would penalize any final analysis dividing our 0.05 alpha in half for each interim analysis.

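### Section 7.3 halves a 0.05 alpha that no planned test uses, while the go decision and its power rest on one-sided P<0.15

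*Combined protocol and SAP*

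**What the plan says.** Section 3.2 sets the primary analysis. The severity scale is compared by a stratified Mann-Whitney test, and a one-sided P below 0.15 "favoring the immune plasma arm will constitute a" go decision. The same threshold opens the subgroup analysis ("If the stratified analysis reaches the go decision"). Section 3.3 and Table 2 give the power of reaching go as 74% and 80%.

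Other analyses in section 3.2 carry no test level. For the secondary variables, "Treatment effects on these variables will be estimated with 95% confidence intervals". Serious adverse events are compared between arms by Fisher's exact test. Section 3.1 places the trial in a larger programme ("This will also serve as an internal pilot in the seamless phase 2/3 study"), and section 3.2 adds, for that later stage, "with possibility that the data in this Phase 2 trial will be included in the final analysis using adjusted" P values. No alpha is given for it. Details of the adjusted analysis and the final SAP "will be determined before unblinding the study data".

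Section 7.3 describes a masked DSMB review of progression to mechanical ventilation, motivated by antibody-mediated enhancement. The DSMB may unmask and require a formal interim at any time, and the number of interims is not capped. The stated outcomes are to interrupt or continue entry or dosing. If the trial continues, "we would penalize any final analysis dividing our 0.05 alpha in half for each interim analysis". The sentence names no test, endpoint or sidedness.

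**The concern.** The penalty refers to an alpha that the rest of the plan does not contain. On its face it reaches every final analysis, and the go test is one. An analyst who follows the sentence literally would judge the go decision at 0.025 after one interim. An analyst who follows section 3.2 would judge it at one-sided 0.15. The documents do not say which prevails.

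What is at stake is the trial's main decision. A result with P between 0.025 and 0.15 would be a go under one reading and a no-go under the other, because a safety question had been asked along the way. If the choice is made once results are known, it is a data-dependent choice of threshold.

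**Working it through.** **Inputs.** From section 3.1: 100 plasma, 50 control. From Table 2, in scale order 1 to 7:
- Scenario 1: control 0, 0, 70, 10, 10, 5, 5%; plasma 0, 0, 82, 7, 6, 3, 2%.
- Scenario 2: control 60, 0, 28, 4, 4, 2, 2%; plasma 75, 0, 19, 2, 2, 1, 1%.

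The plasma columns fit the stated shift odds ratio of 2. For the first non-empty category, 2×0.70/(0.30+2×0.70) = 0.82 and 2×0.60/(0.40+2×0.60) = 0.75.

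**Test.** With N = 150, let W be the sum of plasma mid-ranks and t_k the number of participants in category k.
- Mean: E = 100×(N+1)/2.
- Variance: V = (50×100/12) × [(N+1) − Σ(t_k³ − t_k)/(N(N−1))].
- Statistic: Z = (E − W)/√V, with go if Z exceeds the upper-α normal quantile.

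Power is the share of simulated multinomial trials that reach go (1,000,000 per case, Monte Carlo error at most 0.05 points). A separate run of the stratified form with 1, 2 and 4 equal strata gave the same power to within about 0.2 points.

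**Step 1: reproduce the plan's figure.** One-sided 0.15 gives 74.1% / 80.9%, against 74% / 80% stated. One-sided 0.05 gives 52.7% / 61.2%, and two-sided 0.05 (0.025 per side) gives 40.8% / 49.2%. The design was sized at one-sided 0.15.

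**Step 2: apply the penalty literally.** After k interims the level is 0.05/2^k, that is 0.025 for k = 1 and 0.0125 for k = 2.

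| Go threshold | Scenario 1 | Scenario 2 |
|---|---|---|
| One-sided 0.15 (section 3.2) | 74.1% | 80.9% |
| One-sided 0.025 (one interim) | 40.8% | 49.2% |
| Two-sided 0.025 (one interim) | 30.8% | 38.5% |

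The loss at one-sided 0.025 is 74.1 − 40.8 = 33.3 points and 80.9 − 49.2 = 31.7 points. Two interims at one-sided 0.0125 give the same power as the last row, because two-sided 0.025 puts 0.0125 in the plasma direction.

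**Step 3: how often it would matter.** The figures above are taken over all trials, but the penalty applies only after a formal interim. The trigger is not defined, so one has to be assumed. Take a plasma excess in categories 6–7 at half enrolment, under the Table 2 effects (Scenario 1 / 2):
- At least 4 points: fires in 11% / 10% of trials. Trials that fire and also have P between 0.025 and 0.15 are about 3.6% / 3.6% of all trials.
- At least 8 points: fires in 2.6% / 0.6%. The affected share is 0.7% / 0.2%. Among the trials that fire, power at 0.15 is already only 38% / 59%.

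The shares are larger if a difference in either direction can call the interim.

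**Step 4: does the go test need a penalty?** Suppose the interim cannot itself declare a go, and a trial halted there is not counted as one. Under no effect, P(go) = P(not halted and P<0.15) ≤ P(P<0.15). The last term is 15.0% / 15.1% in simulation. The go hypothesis is tested once, so the interim adds no false-go error.

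**The case against.** The strongest reply is that the 0.05 was never meant for the go test. Section 3.2 uses the term final analysis for the later Phase 3 stage and calls the Phase 2 comparison the primary analysis. Alternatively, the 0.05 could attach to a secondary outcome close to the interim endpoint (section 3.1 lists times to event "including time to death, time to requiring critical care, and time to requiring hospitalization") or to the Fisher's exact comparison. Under any of these the go decision is untouched. These readings are plausible, but section 7.3 states none of them. Its wording reaches every final analysis, and no alpha is given for Phase 3.

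A second reply is that the final SAP is still to come. That does not cancel a conflicting rule already written. Nor does section 3.2 say whether DSMB unmasking counts as unblinding.

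Several stronger readings are tempting, and the documents do not support them:
- A reader might infer that about a third of trials are affected, from the 33.3- and 31.7-point losses. Those figures ignore whether an interim took place. Under the assumed triggers the share is 3.6% or less.
- A reader might infer that the interim can stop only for harm. Enhancement is the stated motive, but section 7.3 asks about a difference between arms without a direction, section 7.1 has the DSMB review efficacy as well, and ventilation is part of category 6. The case for leaving 0.15 alone rests instead on the interim having no stated route to a go claim.
- A reader might infer that the go level is to be halved to 0.075. Nothing in the text halves 0.15.
- A reader might call 0.15 the plan's only decision rule of any kind. Section 7.3 also has event-based halting rules; 0.15 is the only statistical efficacy rule.

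**Conclusion.** The conflict holds. Section 7.3 applies a penalty to a 0.05 alpha that belongs to no defined test, while the go decision and its stated power rest on one-sided 0.15. Read literally, one interim moves the go threshold to 0.025 and unconditional power to about 41% / 49% one-sided or 31% / 38% two-sided. If the 0.05 belongs elsewhere, nothing changes for the go decision.

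The problem depends on a formal interim being held and the trial continuing. It is conservative: it cannot create false go decisions, but it can turn a go into a no-go. How often cannot be fixed from the documents, because the trigger is undefined. The share of 3.6% or less assumes a plasma-excess trigger of 4 or 8 points at half enrolment and the Table 2 effects. It should be fixed because it concerns the main decision threshold and is cheap to settle.

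**What to change.** Before any DSMB unmasking, reconcile sections 3.2 and 7.3:

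1. State in section 7.3 that the ventilation interim cannot produce a go or efficacy claim, so the one-sided 0.15 go threshold is unchanged by it, and cross-reference this in section 3.2.
2. Name the analysis, level and sidedness to which the 0.05 penalty applies, whether secondary, safety or later Phase 2/3.
3. If the sponsor does want a penalty on the go decision, state the resulting one-sided level and restate the section 3.3 power at that level.

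The cost is two or three sentences in section 7.3 and a cross-reference in section 3.2, with no patients and no extra data. Power needs restating only under item 3.
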